## **SECONDARY ENDPOINT**

All secondary end points will be assessed pre-MSC infusion at days 0, 30, and 60, and also at days 90, 180, and 360. In addition, blood will be drawn 1 week after each infusion for potential biomarker analysis, depending on analysis of pre-infusion data. These 1-week post infusion blood samples will be frozen and stored.

### **Efficacy**

#### 1. Change in the following inflammatory cytokines at 90 days:

CD14, CD163, CD40, CRP, E-Selectin, Fas, (TNFRSF6/Apo-1), Fas Ligand (TNFSF6), GCSF, ICAM-1 (CD54), IL-1 alpha (IL-1 F1), IL-1 beta, IL-1 R4, IL-10, IL-12 p70, IL-13, IL-18, IL-2, IL-2 R alpha, IL-4, IL-6, IL-8, Lipocalin-2, MCP-1, MCP-2, MIF, MIP-1 alpha, MIP-1 beta, Osteopontin, PAI-1, Platelet Factor 4, Procalcitonin, RAGE, Resistin, Thrombomodulin, TNF alpha, TREM-1, Troponin I, uPAR, VCAM-1, VEGF-A using a biomarker array kit.

#### 2. NK cell depletion, defined as % reduction in NK cells from baseline to day 90.

## **EXPLORATORY ENDPOINTS**

1. Change in the following cardiac biomarkers: N-Terminal Prohormone of Brain Natriuretic Peptide (NT-proBNP) and soluble suppression of tumorigenicity 2 (sST2) between baseline and day 90 post initial infusion.
2. Change in RV systolic function and volumes assessed by 2D and 3D echocardiography and gated blood pool SPECT ventriculography scan between baseline and day 90 post initial infusion.
3. Hospitalizations due to right HF (as defined by INTERMACs) at day 90.
4. 6 minute walk distance changes between baseline and day 90 post initial infusion.
5. Change in Quality of life (Kansas City Cardiomyopathy Questionnaire; KCCQ) between baseline and day 90 post initial infusion.

## 6. Frequency and severity of gout flares at day 90.

### 4.3 Safety Plan

The safety of subjects will be carefully monitored by the investigators and reviewed by an independent Data and Safety Monitoring Board (DSMB). Details of AE description and procedures for reporting are detailed in section 8.

### 4.4 Compliance with Laws and Regulations

This study will be conducted in accordance with the International Conference on Harmonisation (ICH) E6 Guideline for Good Clinical Practice (GCP), the principles of the Declaration of Helsinki (October 1996) and applicable local, state, and federal laws, as well as other applicable country laws.

## 5 STUDY ENROLLMENT

Subjects will participate in this study for about 360 days as follows: Patients will be deemed enrolled once the patient is randomized.

### 5.1 SUBJECT SELECTION

The study will enroll at least 30 subjects and will consist of 2 cohorts. Enrolled subjects will be randomized at 1:1 into an experimental group (n=15) or a placebo group (n=15), stratified by LVAD type. Subjects in the experimental group will receive 1.5 million cells per kg, and subjects in the placebo group will receive 1.5 mL/kg Lactated Ringer's Solution at day 0 ( $\pm 7$  days), day 30 ( $\pm 7$  days) and day 60 ( $\pm 7$  days).

Subjects will be selected using the following inclusion and exclusion criteria:

#### INCLUSION CRITERIA

1. Age  $\geq 18$  years.
2. One of the two following HF etiologies:
  - a. Ischemic HF etiology, defined as 1) a prior history of myocardial infarction and/or 2) angiographically or cardiac CTA documented significant CAD (defined as a prior history of coronary revascularization (CABG or PCI) and/or obstructive CAD ( $\geq 75\%$  stenosis of the left main or proximal LAD or  $\geq 75\%$  stenosis of two or

more major epicardial coronary arteries)) prior to LVAD implantation (any coronary angiogram ever prior to LVAD implantation can be used, but an angiogram is not required to confirm non-ischemic etiology, imaging is acceptable).

- b. Non-ischemic cardiomyopathy
3. Advanced HF defined as HF requiring LVAD implantation and deemed stable on his/her LVAD.
4. On stable medical therapy (per the discretion of the treating physician) including beta-blockers, ACE-inhibitors, angiotensin receptors blockers, angiotensin receptor neprilysin inhibitor, mineralocorticoid receptor antagonists, isosorbide, hydralazine, and mineralocorticoid receptor antagonists) and optimized pump speed for at least a month prior to randomization.
5. HS-CRP level  $\geq 2$  mg/l.
6. NYHA class II-III symptoms.
7. Ability to understand and provide signed informed consent.
8. Reasonable expectation that patient will receive standard post-treatment care and attend all scheduled safety follow-up visits.

## **EXCLUSION CRITERIA**

1. Women of childbearing potential. Postmenopausal women or women with permanent contraception method (defined as total hysterectomy) will not be excluded.
2. History of debilitating stroke (modified Rankin Score  $> 3$ ) within 3 months.
3. The likelihood of requirement of cardiac surgery during the study period.
4. Presence of clinically significant, uncorrected left sided valvular heart disease, active acute myocarditis, or uncontrolled hypertension defined as Persistently elevated mean arterial blood pressure ( $>100$  mmHg). Echocardiography within 12 months of screening. Patients can be re-evaluated, at the discretion of the investigator.
5. QTc  $>550$  ms (in the absence of bundle branch block, interventricular conduction delay or ventricular pacing). Electrocardiogram (ECG) within 60 days.

6. History of cardiac arrest within 3 months.
7. Hypertrophic or infiltrative cardiomyopathy.
8. Considered or listed for organ transplantation or history of organ transplantation
9. Illness other than HF with life expectancy less than 12 months.
10. Enrolled in an interventional trial or received an experimental drug or device within 30 days of randomization.
11. Biventricular assist device (Bi-VAD) support.
12. Severe COPD defined by FEV1<1L, and FEV1/FVC<70% within 12 month if known history of COPD, otherwise FEV1<1L, and FEV1/FVC<70% within 24 months
13. Uncontrolled seizure disorder.
14. Clinically significant hematologic, hepatic, or renal impairment as determined by screening clinical laboratory tests within the last 30 days:
  - Liver disease = ALT or AST > 3x normal, alkaline phosphatase or bilirubin >2x normal
  - Renal disease = End stage renal disease on long term dialysis Hematologic = Unexplained persistent leukocytosis (WBC >11 K/UL) or hemoglobin < 8.5 gm/dl
15. Presence of any other clinically-significant medical condition, psychiatric condition, or laboratory abnormality, that in the judgment of the investigator or sponsor may affect compliance with the study protocol or pose a safety risk to the subject.
16. Inability to comply with the conditions of the protocol.
17. Acute coronary syndrome within 4 weeks (clinical diagnosis, confirmed by electrocardiographic abnormalities and elevation of troponin-I).
18. Malignancy within the previous five years, except adequately treated basal cell carcinoma, provided that it is neither infiltrating nor sclerosing, and carcinoma in situ of the cervix
19. Active uncontrolled systemic infection. Positive blood or deep tissue cultures or clinical or imaging evidence of systemic infection despite complete course of effective antimicrobial therapy as determined by infectious diseases. Localized (non-systemic) infection is not an exclusion criterion.

Patients can be re-evaluated, at the discretion of the investigator.

20. Early postpartum cardiomyopathy (within six months of diagnosis).
21. Presence of inherited or acquired immune deficiency or human immunodeficiency virus infection (HIV). Negative HIV test within the preceding 12 months is required.
22. Systemic corticosteroids, immunosuppressive drug therapy (cyclophosphamide, methotrexate, cyclosporine, tacrolimus, azathioprine, mycophenolate, sirolimus, etc.), and DNA depleting or cytotoxic drugs taken within four weeks prior to study treatment.
23. Known Porphyria.
24. Allergy to sodium citrate or any “caine” type of local anesthetic.
25. Patient enrolled in hospice care.

## **5.2 Method of Treatment Assignment and Blinding**

This study is a Phase IIa, double-blind, placebo-controlled, multi-site (up to 2), randomized trial comprised of 30 subjects with an experimental group (stem cell infusion; n=15) and a placebo group (n=15; LRS at a volume of 1.5 mL/kg). Each group will receive 3 repeated doses of the assigned treatment (no cross-over) at times 0, 30 and 60 days. The infusion bags of stem cells or placebo will be identical.

In the event that a patient is unable to receive an infusion on or within the window of 30 or 60 days, the earliest infusion will be scheduled once it has been deemed safe for infusion. The primary endpoint measurement at day 90 (or within window) will remain irrespective to the number of infusions completed. More specifically, if infusion #2 (day 60) is missed then it will be scheduled as soon as the patient is deemed stable. The infusion #3 will occur 30 days from infusion # 2 but before day 90 (plus window) primary endpoint imaging evaluation. In the event that infusion # 3 would fall after the upper bound of the 90 day primary endpoint window then this infusion will be skipped.

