### **Administration of Human Allogeneic MSCs**

The study will enroll a minimum of 30 subjects and will consist of 2 cohorts. Enrolled subjects will be randomized at 1:1 into an experimental group (n=15) or a placebo group (n=15). Subjects in the experimental group will receive 1.5 million cells per kg, and subjects in the placebo group will receive 1 mL/kg LRS at days 0, 30 and 60.

After the subject is randomized into one of the two cohorts, the final formulation of MSC or placebo will be prepared. Within 8 hours of infusion, the appropriate number of cells will be thawed at the study site pharmacy and re-suspended in LRS at a concentration of  $1 \times 10^6$  cells/mL. Subjects in placebo group will receive LRS at a volume of 1.5 mL/kg. The study solution (MSCs or placebo) will be labeled to ensure investigator blinding. The solution will be labeled to indicate that it is an investigational agent and will contain subject's identifying information, date, and time of formulation.

An intravenous line will be placed into a peripheral vein, and 0.9% sodium chloride solution will be run to keep the vein open. The study product will be drawn using an 18-gauge needle into a 60 mL syringe with an eccentric tip. The needle will be removed, and infusion tubing will be attached to the syringe. The syringe with infusion tubing will be placed in a metered dose syringe pump positioned horizontally with the syringe rotated such that the syringe tip is at the lowest position. The product will be infused intravenously into the subject's arm at a constant rate of approximately 2 mL/min. The applicable volume for the target dose will be delivered within  $\pm 2$  mL. Depending on subject's weight, up to three 60 ml syringes of product may be infused. After the entire product volume is delivered, 25 mL of LRS (without cells) will be infused at 2 ml/min to deliver cells from the infusion line for more accurate dosing. Subjects in the placebo group will receive intravenous LRS. Their syringes will be labeled as above to preserve blinding and followed by 25 ml of LRS infusion as above.

If the subject has an adverse reaction during the infusion, the infusion may be interrupted or slowed according to the severity of the reaction.

The following symptoms, if noted, during infusion may lead to slowing or cessation of the infusion session:

- Temperature  $\geq 39^{\circ}\text{C}$ .
- Unexplainable shaking chills.
- Angioedema.
- Respiratory distress.
- Wheezing/bronchospasms.

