## **6.2 IV Administration of MSCs or Placebo**

An intravenous line will be placed into an appropriate peripheral vein with 0.9% sodium chloride solution running to keep the vein open. The study solution described above will be taken up in an 18 gauge needle into a 60 mL syringe with an eccentric (offset) tip. The needle will be removed and infusion tubing will be attached to the syringe. The syringe with infusion tubing will be placed in a metered dose syringe pump positioned horizontally with the syringe rotated such that the syringe tip is at the lowest position. The product will be infused intravenously into the subject's arm at a constant rate of approximately 2 mL/min. The applicable volume for the target dose will be delivered within 2 mL. Depending on subject's weight, up to three 60 mL syringes of product may be infused. After the entire product volume is delivered, 25 mL of LRS (without cells) will be infused at 2 mL/min to deliver cells from the infusion line for more accurate dosing. Subjects in the placebo group will receive intravenous LRS. Their syringes will be labeled as above to preserve blinding and followed by 25 mL of LRS infusion as above.

If the subject has an adverse reaction during the infusion, the infusion may be interrupted or slowed according to the severity of the reaction. All appropriate treatment will be given to reduce any discomfort and ensure the subject's safety. The infusion may be restarted, if interrupted, if the subject is not considered to be at risk by the Investigator and the subject consents.

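### The blind is stated in terms of identical infusion bags, but the product is given from syringes and tubing, and the protocol describes nothing that masks a cell suspension against cell-free LRS

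*Combined protocol and SAP*

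**What the plan says.** The design is stated in Section 5.2: "This study is a Phase IIa, double-blind, placebo-controlled, multi-site (up to 2), randomized trial comprised of 30 subjects". The same paragraph gives the masking device: "The infusion bags of stem cells or placebo will be identical".

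The preparation and infusion text describes a different container. Under Administration of Human Allogeneic MSCs: "The study product will be drawn using an 18-gauge needle into a 60 mL syringe with an eccentric tip". Section 6.2 repeats it: "The study solution described above will be taken up in an 18 gauge needle into a 60 mL syringe with an eccentric (offset) tip". Both passages then attach tubing and mount the syringe on a pump with its tip at the lowest point. Up to three syringes may be used, depending on weight. Neither passage mentions an infusion bag.

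On contents, for the active arm "the appropriate number of cells will be thawed at the study site pharmacy and re-suspended in LRS at a concentration of" 1 x 10^6 cells/mL. The placebo is LRS.

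On masking at this step, the administration text says: "The study solution (MSCs or placebo) will be labeled to ensure investigator blinding". Section 6.2 says of placebo: "Their syringes will be labeled as above to preserve blinding and followed by 25 mL of LRS infusion as above". The parallel labelling sentence in Section 6.1 does not mention blinding.

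On placebo volume, the administration text gives both 1 mL/kg and 1.5 mL/kg. Sections 4.1, 5.1, 5.2 and 6.1 give 1.5 mL/kg.

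**The concern.** A blind described through one container does not carry over to another. Even if identical bags are the source from which syringes are filled, they mask nothing once the fluid is in a syringe and a line. A label identifies a syringe without hiding what is in it, and the contents differ by arm in the one respect that could be visible: one holds suspended cells.

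The stake is the assessments that depend on judgement. Safety is the primary objective (Section 3.1). Section 8.1.1 has clinicians grade the severity of every adverse event and judge its relationship to the product, and Section 9.2 tabulates incidence by grade and by relationship and compares it with Fisher's exact test. Investigators also decide during the infusion whether a reaction warrants slowing or stopping, so they may be near the syringe. KCCQ is self-reported and the 6-minute walk depends on effort; both are exploratory endpoints at day 90 (Section 4.2).

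Background Section 4 adds context. The earlier trial of this product was single-blind and reported gains in walk distance and KCCQ without a significant change in LV function. That does not show bias, but it explains why a secure double blind matters for these outcomes.

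**Working it through.** The plan states no figure for masking, so there is none to reproduce. The check is to match each stated measure to the container actually used, and then to work out volume and duration.

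**Masking measures against delivery**

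| Measure | Where stated | What it covers at infusion |
|---|---|---|
| Identical bags | Section 5.2 | No bag appears in the infusion steps |
| Label on solution and syringes | Administration text; Section 6.2 | Identity on the label, not appearance |
| Equal 25 mL LRS flush | Administration text; Section 6.2 | Length of the final step |
| Placebo at 1.5 mL/kg | Administration text; Sections 4.1, 5.1, 5.2, 6.1 | Volume and duration, see below |

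The documents mention no opaque sleeve, covered line, screen or appearance-matched placebo. They also do not say that the syringes are left uncovered. Section 6.1 lists appearance as a release test only, and neither product's look is described.

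**Volume and duration**

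Inputs: 1.5 x 10^6 cells/kg, 1 x 10^6 cells/mL, about 2 mL/min, 25 mL flush, 60 mL syringes.

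- Active volume = (1.5 x 10^6 x weight) / 10^6 = 1.5 mL/kg.
- Time = volume / 2 mL/min.
- 70 kg: 105 mL, 52.5 min; with flush 130 / 2 = 65 min.
- 90 kg: 135 mL, 67.5 min; with flush 160 / 2 = 80 min.
- Three syringes hold 180 mL, which covers up to 180 / 1.5 = 120 kg.
- 30 subjects x 3 infusions = 90 infusions.

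**Effect of the two placebo volumes**

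| Weight | Active | Placebo at 1.5 mL/kg | Placebo at 1 mL/kg |
|---|---|---|---|
| 60 kg | 90 mL, 45 min, 2 syringes | 90 mL, 45 min, 2 syringes | 60 mL, 30 min, 1 syringe |
| 80 kg | 120 mL, 60 min, 2 syringes | 120 mL, 60 min, 2 syringes | 80 mL, 40 min, 2 syringes |
| 100 kg | 150 mL, 75 min, 3 syringes | 150 mL, 75 min, 3 syringes | 100 mL, 50 min, 2 syringes |

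Under the 1.5 mL/kg text, volume and time are the same in both arms and give no cue. Under the 1 mL/kg text, placebo would finish in two thirds of the time and sometimes use one syringe fewer.

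**The case against.** A reader might infer that the syringes are uncovered and that patients and staff can see which arm they are in. The documents do not support that. They are silent on covering and on the appearance of either fluid. The flush is given in both arms and is explained by dosing accuracy. The pump instruction, which turns the outlet downwards ("The syringe with infusion tubing will be placed in a metered dose syringe pump positioned horizontally with the syringe rotated such that the syringe tip"), suggests that settling was considered, but not that the suspension is distinguishable by eye. Section 6.1 refers storage and handling to the manufacturer's Pharmacy Manual, which is not among the documents and may contain masking steps. A reader might also infer that draw-up happens at the bedside. Only the order of the sentences, with the line placed first, points that way, and preparation is placed at the site pharmacy. Bags and syringes could also coexist, with one filled from the other.

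The reach of any unblinding is limited as well. Echocardiograms and SPECT scans are read blind (Section 4.1). The secondary endpoints are cytokine and NK-cell assays, many primary safety items are laboratory values, vital signs, ECG and mortality, and NYHA class is not a listed endpoint. Section 8.1.1 says that relationship does not decide whether an event is reported. The analyses are mainly descriptive, and Sections 9 and 9.3 say the study is not powered.

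All of this stands, and it limits the claim to what the protocol fails to assure. It does not remove the mismatch between the stated device and the delivery container, or supply a visual mask. If the Pharmacy Manual contains one, the protocol should cite it.

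**Conclusion.** The point holds in a limited form. The protocol's one statement about identical presentation concerns a container that its infusion steps do not use, and nothing else it describes conceals a cell suspension against cell-free LRS. The double blind is therefore not assured at the bedside. Whether it would actually fail rests on the assumption that the two fluids look different, which the documents neither confirm nor exclude.

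On that assumption, the cue would be available for roughly 53 to 68 minutes of product infusion at 70 to 90 kg, on up to three occasions per subject. The size of any resulting bias cannot be derived from the documents. The outcomes most open to it are adverse event severity and relationship, KCCQ and walk distance.

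Separately, and without any assumption about appearance, the two placebo volumes contradict each other, and one of them would make volume and duration differ by arm. The change should be made: masking cannot be restored once an infusion has been seen.

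**What to change.** 1. Replace the bag sentence in Section 5.2 with the presentation actually used, and align the administration text and Sections 6.1 and 6.2 with it.
2. Require the preparing unit to fill the syringes for both arms and supply them in opaque sleeves, with the infusion line covered too. Alternatively, document that the two products are visually indistinguishable. If the Pharmacy Manual already covers this, cite the step in the protocol.
3. Reconcile the 1 mL/kg and 1.5 mL/kg placebo volumes in the administration text and state one volume throughout.
4. Where existing staffing allows, the person who loads the syringes should not judge adverse event relationship or run the walk test for that subject. This is desirable rather than essential, because making it mandatory might need extra staff.

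The cost is a short amendment plus covers for at most 90 infusions with 30 subjects, or up to 90 x 3 = 270 product syringes. Some sections call 30 a minimum, so the count rises if more are enrolled. The drawback is that residual volume and air bubbles are harder to see through a sleeve; the pump display and a check by the person loading the syringe would have to serve instead.

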## **5.3 Subject Discontinuation and Withdrawal**

Subjects have the right to withdraw from the study at any time. Subjects will be given the option to provide a reason for withdrawal. In case of early withdrawal, the reason for withdrawal will be recorded on the appropriate Case report form (CRF). Attempts to complete early termination exam as defined in 7.4 will be made. The Investigator has the right to discontinue a subject from the study for any medical reason that the investigator determines may jeopardize the subject's safety if he or she continues in the study, or for reasons of noncompliance (e.g., missed visits, use of other investigational drugs, etc.).

#### **5.4 Study Termination**

The Sponsor has the right to terminate the study at any time. Reasons for terminating the study may include, but are not limited to, the following:

- The incidence or severity of AEs in this or other studies indicates a potential health hazard to subjects.
- Unsatisfactory subject enrollment.
- Rate of enrollment of < one subject per 3 months.
- An excess drop out of subjects (a total of  $\geq 5$  subjects per each arm, but not due to VAD –related mortality).
- Inaccurate or incomplete data recording.
  - $\geq 20\%$  missing data for the primary safety endpoints.
  - $\geq 30\%$  missing data for the efficacy endpoints.

### **6. INVESTIGATIONAL PRODUCT**

#### **6.1 Formulation, Packaging, Preparation, Randomization of MSCs or Placebo**

The final product will be stored and handled as described in Stemedica's Pharmacy Manual (referenced in their Investigator's Brochure).

The product being administered to the patient is the exact product being referenced in IND 14328 and will not be altered prior to use.

The following tests--gram stain, endotoxin, cell count, viability, and appearance--will be conducted with final results available prior to administration of the drug per Stemedica's formulation protocol. Sterility testing is

conducted per USP requirements by an approved testing lab for sterility testing after thawing the product, with results available post administration to the patient.

Endotoxin, appearance, and gram testing are done by our collaborators at the Cell Processing Lab at Children's Hospital (Cellular Therapy Lab) prior to administration. This Laboratory is located across the street from the MedStar Washington Hospital Center, where patient processing is performed and the cells will be infused. The only test that will not be available prior to patient administration is the sterility test.

The following steps will be followed:

1. The Cellular Therapy Lab will send samples to an approved testing lab for sterility testing by BacT/Alert (culture for 14 days bacterial, 21 day fungal) immediately after thawing the product.
2. Retention samples will be sent from the Cellular Therapy Lab to Medstar when the product is transported.

The Medstar clinical trial team will keep the retention samples (in case sterility results come back positive).

3. If sterility test is negative the retained sterility sample will be destroyed.
4. If sterility test is positive (i.e. the sample is not sterile) the following action plan will be followed.

Action plan for a positive sterility testing:

1. Microbiology testing lab will notify the PI, the clinical trial manager or designee, and the Cellular Therapy Lab of any positive cultures immediately.
2. Further testing for organism speciation and antibiotic sensitivity will be conducted by the microbiology lab and reported to the PI in a timely fashion to guide patient management.
3. The PI is responsible for ensuring patient safety and will ensure that the patient is notified of the test results, assessed for adverse events and treated in a timely fashion as medically appropriate.
4. The PI/designee will notify Stemedica point person within 24 hours of receipt of report from lab.
5. The PI will determine whether the FDA and IRB need to be notified immediately (e.g. if there is a serious adverse event) or if this will be included in the progress report. Standard reporting of adverse events will be followed as specified in the protocol.
6. The notification and workup for positive culture form will be completed (form attached).
7. All products with positive cultures will be marked with a biohazard label.

8. The retention sample will be sent to the microbiology lab for testing.
9. All the materials will be maintained until further instruction is received from Stemedica.
10. Stemedica staff to investigate failure and determine if further formulation activities or testing is required to support investigation of the issue.

The study will enroll a minimum of 30 subjects and will consist of 2 cohorts. Enrolled subjects will be randomized at 1:1 into an experimental group (n=15) or a placebo group (n=15). Subjects in the experimental group will receive 1.5 million cells per kg and subjects in the placebo group will receive 1.5 mL/kg Lactated Ringer's Solution.

Once the subject is randomized into one of the two cohorts, the cells or placebo will be prepared. Within 8 hours of infusion, the appropriate number of cells will be thawed at the study site pharmacy and re-suspended in Lactated Ringer's Solution (LRS) at a concentration of  $1 \times 10^6$  cells/mL. Subjects in placebo group will receive LRS at a volume of 1.5 mL/kg. The study solution (cells or placebo) will be labeled to indicate that it is an investigational agent and will contain a subject's information, date, and time of formulation.

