Changes in the severity of an AE will be documented to allow an assessment of the duration of the event at each level of intensity to be performed. AEs characterized as intermittent require documentation of onset and duration of each episode.

**Relationship to Study Products:** The clinician's assessment of an AE's relationship to investigational product is part of the documentation process, but it is not a factor in determining what is or is not reported in the study. If there is any doubt as to whether a clinical observation is an AE, the event will be reported. All AEs must have their relationship to investigational product assessed. In a clinical trial, the investigational product must always be suspect. To help assess, the following guidelines are used.

- Related – There is a plausible temporal relationship between the onset of the AE and administration of the investigational product, and the AE cannot be readily explained by the subject's pre-existing clinical state,

intercurrent illness, or concomitant therapies; and/or the AE follows a known pattern of response to the investigational product; and/or the AE abates or resolves upon discontinuation of the investigational product and, if applicable, reappears upon re-challenge.

- Not Related – There is good evidence that the AE has an etiology other than the investigational product (e.g., pre-existing medical condition, underlying disease, intercurrent illness, or concomitant medication); and/or the AE has no plausible temporal relationship to administration of the investigational product (e.g., cancer diagnosed 2 days after treatment).

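### Section 6.1 places retention samples of the thawed cell product with the clinical trial team, with no placebo counterpart and no unblinded custodian, so a sample's presence or absence may reveal the arm.

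*Combined protocol and SAP*

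**What the plan says.** Section 6.1 sets out the sterility workflow. The Cellular Therapy Lab sends a sample for culture "immediately after thawing the product". Next, "Retention samples will be sent from the Cellular Therapy Lab to Medstar when the product is transported". Custody is then assigned: "The Medstar clinical trial team will keep the retention samples (in case sterility results come back positive". After a negative culture, "If sterility test is negative the retained sterility sample will be destroyed". After a positive one, the microbiology laboratory notifies the PI, the trial manager or a designee, and the Cellular Therapy Lab, and the retention sample is sent for testing.

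The same section describes the product in these words: "The product being administered to the patient is the exact product being referenced in IND 14328". Later it says that "the appropriate number of cells will be thawed at the study site pharmacy", as does the section on administration of the cells. Placebo is Lactated Ringer's Solution (LRS) alone.

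The trial is double-blind (sections 4.1 and 5.2). The written safeguards are labelling and identical containers. In the administration section, "The study solution (MSCs or placebo) will be labeled to ensure investigator blinding"; section 6.2 labels the placebo syringes to preserve the blind; section 5.2 makes the infusion bags identical.

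**The concern.** Labels and matching bags protect the dose itself. They do nothing about a second object that arrives with the dose. If that object exists for active doses only and is handed to the team running the trial, its presence suggests MSC and its absence suggests placebo, without any positive culture.

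Safety is the primary objective (section 3.1), and part of it rests on judgement. Clinicians grade the severity of adverse events, and section 8.1.1 requires that "All AEs must have their relationship to investigational product assessed". Section 9.2 then presents adverse-event incidence by grade and by relationship, and compares it with Fisher's exact test. A grader who knows or suspects the arm can shift those tables in either direction, and lost blinding cannot be repaired after dosing. Non-emergency changes of pump speed also need the PI's approval (section 4.1; Concomitant Therapy and Clinical Practice), so knowledge of the arm could reach co-management as well as grading.

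**Working it through.** The plan states no figure to reproduce. The check is a reading of the text plus one count.

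**Step 1. Is the workflow for cells only?** Three things in section 6.1 point that way.
- The culture sample is triggered by thawing, and only cells are described as thawed.
- The product is identified by IND 14328, which points to the cells and not to LRS.
- The tests before release include cell count and viability, which have no meaning for LRS.

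No section describes a culture or retention sample for placebo. None says that placebo has no such sample either.

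**Step 2. Who holds the sample?** The text names the clinical trial team. It does not name the lab, the pharmacy or an unblinded role, and no firewall within the team is described.

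**Step 3. Can a sample be linked to an infusion?** Section 6.1 does not say how samples are labelled. But a sample that is destroyed after a negative culture, or tested again after a positive one, has to be matched to a dose. It also travels when the product travels, so its date of arrival carries information even under a coded label. Section 8.1 separates the infusions of the first five subjects by at least one day. For those subjects in particular, an arrival would point to one person.

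**Step 4. Do the stated safeguards cover it?** Solution labels, syringe labels and identical bags all concern the infused solution. None covers a separate sample.

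**Step 5. Count.** Inputs are 15 subjects per arm (section 4.1) and 3 doses per subject (section 5.2).
- Planned doses per arm: 15 x 3 = 45.
- Case (a), no sham placebo samples and samples linkable to an infusion: up to 45 MSC doses with a sample, against 0 of 45 placebo doses.
- Case (b), matched placebo samples, or coded samples held only by unblinded staff: a sample tells blinded staff nothing.

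The text leans to case (a) but does not settle it. The 45 is a ceiling: section 5.2 allows a late third infusion to be skipped, and section 6.1 describes MedStar only.

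**Step 6. Which outcomes are exposed?**

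| Outcome | Where | Exposure |
|---|---|---|
| AE severity and relatedness | 8.1.1, 9.2 | Direct: investigator judgement |
| 6-minute walk, KCCQ (exploratory) | 4.2 | Some: effort- or report-based |
| Echocardiography, SPECT | 4.1 | Low: blinded core lab, blinded observer |
| Cytokines, NK cells, safety laboratory tests | 4.2 | Low: laboratory measures |
| All-cause mortality | 4.2 | Low |

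**Step 7. Where are the cells thawed?** The sterility steps have the Cellular Therapy Lab send samples right after thaw and then have the product transported. The administration section, and the end of section 6.1, place thawing in the study site pharmacy. The two accounts cannot both describe the same step, and the answer decides who sees unblinded product.

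**The case against.** A reader might infer that the team can identify every MSC subject, or all 30 subjects from the first infusion on. The documents do not support that. It needs three facts that they do not give: that no sham placebo sample is made, that samples can be traced to a subject or date, and that the custodians are among the staff who must stay blinded. Silence about a placebo sample does not prove there is none. Section 6.1 also defers to the manufacturer's Pharmacy Manual for storage and handling. That manual is not part of the documents and could specify coding, custody or matched samples. Section 5.2 allows up to two sites, and the workflow covers one.

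Nor do the documents say that the sample holders are the people who assess adverse events. Section 8.1.1 limits relatedness to an MD, DO, PA or NP, and the trial team may include staff with no assessing role. Subjects do not see the samples, so their own blinding is not directly touched. NYHA class is collected but is not listed as an endpoint in section 4.2, and the walk test is exploratory.

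It is also tempting to say that destruction of the sample confirms the arm. The text does not state who destroys it or who learns of a negative result, so this adds little beyond receipt and custody.

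All of that stands, and it limits the certainty and reach of the point. It does not remove the point. Custody by the trial team is a rule written into the protocol, and nothing in the protocol offsets it.

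**Conclusion.** The concern holds as a route to unblinding that the written workflow opens. It is not shown that unblinding will occur. As section 6.1 stands, a sample described only for active product goes to the team running a double-blind trial, with no matching placebo step and no unblinded custodian.

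The size is conditional: up to 45 MSC doses with a sample against 0 placebo doses, if no sham samples exist and samples can be tied to an infusion. If either matched samples or unblinded-only custody is already in place, the exposure from this route falls to nothing. The consequence is concentrated in the judged part of the primary safety assessment. The conflict over thaw location is a separate inconsistency. It does not itself show that anyone is unblinded, but it bears on who handles the product before it is blinded.

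**What to change.** Amend section 6.1 as follows.

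1. Retention samples, and notice of negative cultures, stay with the Cellular Therapy Lab or a designated unblinded pharmacist and do not go to blinded trial staff.
2. Positive-culture notification to the PI stays as written, and each such notice is logged as a potential unblinding of that subject.
3. Both arms reach the bedside by the same route and with the same paperwork.
4. The place of thawing is stated once, and section 6.1 and the administration section are reconciled to it.

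If the Pharmacy Manual already provides for coding or matched placebo samples, section 6.1 should say so, and its custody sentence should be brought into line.

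The cost is a short amendment and storage with people who must know the allocation anyway in order to prepare the dose. The one downside is that, after a positive culture, the retention sample has to be requested from the lab or pharmacy.
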